### **Reflex assessments**

### Acute effects after dosing: Reflex

On each dosing day, each predosing reflex will be compared with all the post dosing assessments with 24 hours to see if the subject has changed (gained or lost) or maintained, reflexes. For this comparison the pre-dose reflex status will be categorized into two categories: 0 and  $\geq 1$ . For each reflex, visit, pre-dose category the number and proportion of subjects who change or maintained will be presented.

### Acute effects after dosing: Reflex and other assessments

On each dosing day, the shifts from predose assessment on that day to postdose (i.e., from predose to 3, 6 and 24 hours postdose) will be determined and shifts the lowest post dose and the highest post baseline for each dose will be presented.

### Chronic effects: Reflex and other assessments

For each item and subject, the lowest predose post baseline and the highest predose post baseline outcomes will be determined and 'shift' tables showing the shifts from baseline (predose value on Day 1) to the lowest predose post baseline and from baseline to the highest predose post baseline value will be presented. In this analysis, all assessments after the first dose will be considered post baseline visits.

For all the assessments the summary statistics for actual values and change from baseline in each parameter will be presented by treatment group and visit. Line plots for each item mean value for each treatment group at each visit and timepoint will also be presented.

Product: Nusinersen	Statistical Analysis Plan
Study: 232SM203	Version: 3.0 Final

### 7.1.5. ECG

ECGs are to be recorded at Days 1, 15, 29, 135, 183, 279 and 302/ET, predose and post dosing at various time points on dosing days and end predose at 302/ET. The ECGs are assessed at a central reading laboratory and the results provided as external vendor data. On the eCRF the investigator interpretation is collected as normal, abnormal and abnormal AE and the investigator determination will be used in analyses.

The ECG test includes heart rate, QT interval, QTcF interval and RR interval. Summary statistics for actual values and change from baseline in each ECG parameter will be presented by treatment group and visit.

ECGs will be analyzed using two approaches.

### Qualitative analysis

The determination of whether an ECG is abnormal not AE, abnormal AE made by the Investigator will be used for this qualitative analysis.

The number and percentage of subjects with shifts from normal to each of the categorical values denoting an abnormal scan (abnormal not AE, abnormal AE) will be summarized by treatment group. All post baseline data will be used to identify abnormalities, regardless of whether a scheduled or unscheduled visit.

### Corrected Fridericia QT interval QTcF abnormalities (outliers)

QTcF will be examined to determine the incidence of clinically relevant abnormalities. The number of subjects evaluated and the number of subjects with clinically relevant abnormalities will be presented.

The first criteria for clinically relevant post dosing abnormalities (secondary safety endpoint) that will be considered is:

Post baseline QTcF of > 500 msec and Maximum increase from baseline to post baseline QTcF >60 msec.

Other criteria are:

Maximum increase from baseline QTcF > 30 to 60 msec

Maximum increase from baseline QTcF > 60 msec

Maximum post baseline QTcF > 480 to 500 msec

Maximum post baseline QTcF > 500 msec

ECG summaries will be presented for all subjects and for subjects with post baseline. Listings will include both the central and eCRF information.

Product: Nusinersen	Statistical Analysis Plan
Study: 232SM203	Version: 3.0 Final

### 7.1.6. Vital Signs

The analysis of vital signs will be approached in two ways.

Vital signs are to be measured at Screening, predose and at 1, 2, 4, 6, and 24 hours postdose on dosing days (Days 1, 15, 29, 64, 135, 183 and 279) and on Day 302/ET. At each of these times, temperature, heart rate, respiratory rate, systolic and diastolic blood pressure, and pulse oximetry will be measured. If multiple evaluations are on the same visit day and visit time, then the mean of multiple evaluations will be selected for inclusion in the analysis.

### **Acute Effects After Dosing**

On each dosing day, the change in each vital sign from predose on that day to postdose (i.e., from predose to 1 hour postdose, to 2 hours postdose, etc.) will be calculated. Summaries of actual values and change from predose for each dosing day will be presented.

### **Chronic Effects**

To examine for possible chronic effects, the change from baseline (the predose value on Day 1) to the predose value on later dosing days and to Day 302/ET will be determined. Summaries of actual values and change from baseline for subsequent dosing days (Days 15, 29, 64,135, 183, and 279) and for Day 302/ET will be presented.

Vital signs (temperature, pulse, systolic and diastolic blood pressure and pulse oximetry) will also be examined to determine the incidence of potentially clinically relevant abnormalities.

### Shift analysis

The number of subjects evaluated and the number of subjects with potentially clinically relevant abnormalities will be presented. All post baseline data will be used to identify abnormalities, regardless of whether a scheduled or unscheduled visit. The criteria for potentially clinically relevant postdose abnormalities are shown in Table 19 below.

### Table 20: Criteria to determine potentially clinically relevant abnormalities in vital signs.

Vital Sign	Criteria for Abnormalities
Temperature	<36°C >38°C
Pulse	<60 bpm >100 bpm

Product: Nusinersen

Systolic Blood Pressure	<90 mmHg
	>140 mmHg
	>160 mmHg
Diastolic Blood Pressure	<50 mmHg
	>90 mmHg
	>100 mmHg
Weight	7% or more decrease from baseline
	7% or more increase from baseline
Respiratory Rate	<12 breaths/min
	>20 breaths/min

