#### **Per Protocol Set**

A Per Protocol Set will include the subset of the ITT Set who have no significant protocol deviations that would be expected to affect efficacy assessments.

Significant protocol deviations will be determined prior to database lock and will include:

Participants who have an SMN copy number other than 2, participants who were greater than 7 months of age at Screening, age of onset of clinical sign >180 days, participants who had hypoxemia at baseline (< 96% at an altitude of < 1500 meters, < 92% at an altitude of 1500 to 2000 meters, or < 90% at an altitude > 2000 meters at Screening).

Participants who are on permanent ventilation or tracheostomy at Screening.

Participants who took experimental or approved agents for the treatment of SMA, including gene therapy, biological agent, or device, during the study. This includes marketed agents at experimental doses that are being tested for the treatment of SMA (oral albuterol/salbutamol, riluzole, carnitine, sodium phenylbutyrate, valproate, hydroxyurea, etc.).

Participants who had a previous diagnosis that would confound the data/conflict with SMA.

If participants have missed planned doses/sham but still completed study.

Product: Nusinersen	Statistical Analysis Plan
Study: 232SM203	Version: 3.0 Final

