### 7.1.7. Growth parameters

Growth parameters include length for age, weight for age, weight for length, head circumference for age, chest circumference, head to chest circumference ratio, and arm circumference.

The growth parameters are to be assessed during screening, on dosing days (Days 1, 15, 29, 64, 135, 183 and 279) and on Day 302/ET.

The weight for age and length for age will be summarized using the WHO child growth standards (WHO Child Growth Standards, 2006) for subjects aged up to 5 years and similarly the WHO growth reference data (WHO, 2007) for older subjects. These standards comprise percentiles for weight and length for age by sex and are available on a website (www.who.int) in txt files. Subjects will be cross referenced with these files, given the age and sex of the subject to determine below which percentile they lie for each parameter.

Summary statistics for actual values and change from baseline in each growth parameter will be presented by treatment group and visit.

Baseline growth parameters will be summarized and also the frequency and percentage for weight and length for age will also be presented for each of in the following categories:  $\leq 1$  st,  $\leq 3$  rd,  $\leq 5$  th,  $\leq 15$  th,  $\leq 25$  th,  $\leq 50$  th and > 50 th percentile.

[figure not shown]
Product: Nusinersen	Statistical Analysis Plan
Study: 232SM203	Version: 3.0 Final

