# 2.2. Study Design

This 3-part study will evaluate the efficacy and safety of a higher dosing regimen of nusinersen in approximately 145 participants. The study will be conducted at approximately 65 sites

Product: Nusinersen	Statistical Analysis Plan
Study: 232SM203	Version: 1.0 Final

globally. Following the completion of this study, all eligible participants may elect to enrol in a separate long-term extension study (232SM302), pending study approval by ethics committees and the appropriate regulatory authorities. In regard to participants rolling over from Part B, this will be done without unblinding the participant's treatment group.

In Part C, up to approximately 40 participants who have already initiated treatment with nusinersen and have been receiving the approved dose of 12 mg for at least 1 year prior to entry will be enrolled in Part C. The initial cohort in Part C (i.e., Cohort 1) consists of up to approximately 20 participants of any age and of any SMA status. For Cohort 1, an attempt will be made to enroll at least 8 but no more than 12 participants  $\geq$  18 years of age (participants in Cohort 1 > 18 years of age must be ambulatory). Up to 5 participants with severe scoliosis and/or severe contractures may be enrolled in Cohort 1 of Part C after consultation with the Medical Monitor. An additional cohort (i.e., Cohort 2) consisting of up to approximately 20 adult participants ( $\geq$  18 years of age) was subsequently added to Part C in Protocol Version 5, in order to enable collection of data in adults transitioning from the currently approved nusinersen dosing regimen to a higher dose. Participants in Cohort 2 can be either ambulatory or non-ambulatory. All participants in Part C will receive a single bolus dose of 50 mg (which should be administered 4 months  $\pm$  14 days after their most recent maintenance dose of 12 mg) followed by 2 maintenance doses of 28 mg on Days 121 and 241. Participants in Part C will remain at the clinic for at least 24 hours after the first (bolus) dose for the purpose of completing study assessments.

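### In the infantile-onset SAP, three fixed vital-sign limits shared with adults (pulse >100, respiratory rate >20, weight gain of 7% or more) would flag nearly every infant, so those rows cannot separate the doses

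*SAP*

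**What the plan says.** **The limits.** Table 20 (infantile-onset SAP, Section 7.1.6) sets pulse at "<60 bpm >100 bpm", the upper respiratory-rate limit at ">20 breaths/min" and the weight-gain criterion at "7% or more increase from baseline". None refers to age.

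**Where else they apply.** The vital-sign tables in the later-onset SAP (Section 6.1.5) and the Part C SAP (Section 5.7.5) repeat every row.

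**The populations.** The infantile-onset Per Protocol Set definition (Section 3.6.1) treats as a significant deviation "participants who were greater than 7 months of age at Screening". The later-onset Per Protocol Set definition implies ages 2 to 10 years. Section 2.2 of the Part C SAP describes "An additional cohort (i.e., Cohort 2) consisting of up to approximately 20 adult participants".

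**The counting rule.** The Shift analysis paragraph of Section 7.1.6 says: "All post baseline data will be used to identify abnormalities, regardless of whether a scheduled or unscheduled visit". It reports the number of subjects evaluated and the number with an abnormality. It does not require the baseline value to lie within limits.

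**The schedule.** Vital signs are taken "predose and at 1, 2, 4, 6, and 24 hours postdose on dosing days (Days 1, 15, 29, 64, 135, 183 and 279"), and at Screening and Day 302/ET.

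**The endpoint.** Section 2.1 lists shifts from baseline in vital signs as a secondary safety endpoint.

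**An age-referenced method in the same SAP.** Section 7.1.7 states: "The weight for age and length for age will be summarized using the WHO child growth standards".

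**The concern.** Young infants, school-age children and adults share one set of fixed limits, and no rationale is given. If a limit lies inside the usual range of a population, almost every subject crosses it at least once over many readings, and the count then says nothing about treatment. For weight, steady growth over ten months is enough to trigger the flag.

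The counting rule adds to this. The paragraph is headed as a shift analysis, but for pulse and respiratory rate it counts a subject whose value was already outside the limit at baseline, which is not a shift. The laboratory section of the same SAP (7.1.3) works differently: its percentages use only subjects at risk of the shift. What is at stake is whether three rows of the vital-sign abnormality table can help compare 12/12 mg with 50/28 mg.

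**Working it through.** The SAP states no expected incidence for this table, so there is no figure to reproduce.

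**1. Tables side by side.** Temperature, pulse, systolic and diastolic pressure, weight and respiratory rate carry the same limits in all three SAPs. This comes from the documents alone.

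**2. Post-baseline readings per infant.** Six readings (predose and five postdose) on each of 7 dosing days, less the Day 1 predose baseline, plus Day 302: 7 × 6 − 1 + 1 = 42. This applies to pulse and respiratory rate. Weight is measured with the growth parameters at screening, on dosing days and at Day 302.

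**3. Chance of at least one flag, treating readings as independent.** With p the chance that one reading crosses the limit, the formula is 1 − (1 − p)^42. The SAP does not give p, so a range is shown.

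| p per reading | Share ever flagged | Expected of 75 infants |
|---|---|---|
| 1% | 34.4% | 25.8 |
| 2% | 57.2% | 42.9 |
| 5% | 88.4% | 66.3 |
| 10% | 98.8% | 74.1 |
| 20% | 99.99% | 75.0 |

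Saturation thus needs a limit that is crossed in roughly 5 to 10% of readings or more.

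**4. Allowing for readings clustered within infants.** Normal simulation, 42 readings each. Assumed between- and within-infant SDs are 12 and 10 bpm for pulse, and 5 and 4 breaths/min for respiratory rate.

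| Assumed mean pulse (bpm) | Ever >100 | Assumed mean respiratory rate (/min) | Ever >20 |
|---|---|---|---|
| 100 | 95.6% | 20 | 94.9% |
| 110 | 99.4% | 25 | 99.5% |
| 120 | 99.96% | 30 | 99.98% |
| 140 | 100% | 40 | 100% |

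The first line puts the mean exactly at the limit. Higher means flag more infants.

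**5. Weight.** The gain that triggers the flag is 0.07 × baseline weight. Day 1 to Day 302 is 301 days. Baseline weights are assumed.

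| Baseline (kg) | 7% gain (g) | g/day needed by Day 302 | Days to reach it at 10 g/day |
|---|---|---|---|
| 4 | 280 | 280/301 = 0.93 | 28 |
| 6 | 420 | 420/301 = 1.40 | 42 |
| 8 | 560 | 560/301 = 1.86 | 56 |

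**6. What saturation leaves to compare.** The planned groups are 25 (12/12 mg) and 50 (50/28 mg). If 95% of controls are flagged, the largest possible excess in the other group is 5 percentage points, and one control infant is already 1/25 = 4 points. As an illustration only, since the SAP plans no test here: with control rates of 90%, 95% and 99%, a two-proportion comparison would have 58%, 38% and 15% power to detect a rise to 99.9%.

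**The case against.** The strongest reply concerns scope.

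- **Other rows still work.** The argument does not touch temperature, low pulse, low respiratory rate, high blood pressure or weight loss of 7% or more, some of which point in safety-relevant directions. A reader might infer that the whole table cannot show a safety signal. The documents do not support that. The low blood-pressure rows were not examined here.
- **Other displays carry the information.** Section 7.1.6 also summarises actual values and change from predose on each dosing day, and change from baseline to later dosing days and Day 302/ET. Section 7.1.7 summarises growth by group and visit on WHO standards. This stands and limits the consequence.
- **A reversed signal is not shown.** A reader might infer that the weight-gain row would count against the dose whose infants survive and grow better. If nearly all infants in both groups are flagged, little contrast remains to reverse. Gain and loss are separate rows. The sample-size section assumes only an additional 3% survival over 12 mg, and no growth difference between doses is given.
- **The table is descriptive.** No safety endpoint is in the testing hierarchy, so the power figures above only illustrate the ceiling.
- **The size rests on outside inputs.** Infant pulse, respiratory rate and weight are not in the SAP, and these infants may feed poorly: the baseline section records feeding difficulties and gastrointestinal tubes. That is fair, and it is why ranges are shown. The weight result needs under 2 g/day across the assumed range. The pulse and respiratory-rate results hold even with the mean at the limit.

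**Conclusion.** The point holds for three criteria in the infantile-onset SAP: pulse above 100 bpm, respiratory rate above 20 breaths/min and weight gain of 7% or more. Two facts are certain from the documents: the limits are the same as those used for older children and for a population with adults, and any post-baseline value counts without a normal-baseline condition. The near-universal flagging is conditional on three assumptions: mean pulse of 100 to 140 bpm, mean respiratory rate of 20 to 40/min with the SDs above, and baseline weight of 4 to 8 kg with even slow growth among infants who stay in follow-up. Across those ranges about 95% to 100% of infants are flagged for pulse and for respiratory rate, and the weight limit is passed at 0.9 to 1.9 g/day. Those rows then cannot discriminate between the doses.

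The consequence is confined to a descriptive table that serves a stated safety endpoint. Efficacy testing, including the primary analysis, is unaffected. The change is worth making because the rows are uninformative by construction and the remedy is cheap.

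**What to change.** Before unblinding, amend Section 7.1.6 and Table 20 of the infantile-onset SAP:

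1. Replace the fixed infant limits with age-referenced limits set by the sponsor's safety physician. No threshold is proposed here.
2. Replace the 7% weight-gain flag with a change in WHO weight-for-age percentile, using the standards already applied in Section 7.1.7.
3. Count a shift only among subjects not already abnormal in that direction at baseline, as the laboratory section does. Section 6.1.2 of the later-onset SAP has the cleaner wording to copy, because Section 7.1.3 repeats its shift-to-high sentence with the wrong baseline condition.
4. Review whether the same limits suit the paediatric participants in the later-onset and Part C tables. No incidence was worked out for those groups.

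Two slips can be corrected in the same edit. The Shift analysis paragraph cites Table 19 but the table is headed Table 20. The Chronic Effects paragraph promises a pulse-oximetry abnormality review for which Table 20 has no criterion.

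The cost is a one-time agreement on the limits and a small programming change. No new data are needed.

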### 7.1.7. Growth parameters

Growth parameters include length for age, weight for age, weight for length, head circumference for age, chest circumference, head to chest circumference ratio, and arm circumference.

The growth parameters are to be assessed during screening, on dosing days (Days 1, 15, 29, 64, 135, 183 and 279) and on Day 302/ET.

The weight for age and length for age will be summarized using the WHO child growth standards (WHO Child Growth Standards, 2006) for subjects aged up to 5 years and similarly the WHO growth reference data (WHO, 2007) for older subjects. These standards comprise percentiles for weight and length for age by sex and are available on a website (www.who.int) in txt files. Subjects will be cross referenced with these files, given the age and sex of the subject to determine below which percentile they lie for each parameter.

Summary statistics for actual values and change from baseline in each growth parameter will be presented by treatment group and visit.

Baseline growth parameters will be summarized and also the frequency and percentage for weight and length for age will also be presented for each of in the following categories:  $\leq 1$  st,  $\leq 3$  rd,  $\leq 5$  th,  $\leq 15$  th,  $\leq 25$  th,  $\leq 50$  th and > 50 th percentile.

[figure not shown]
Product: Nusinersen	Statistical Analysis Plan
Study: 232SM203	Version: 3.0 Final

### 7.1.8. LP opening pressure

LP opening pressure will only be measured at Days 1, 15, and 279 to avoid potential unblinding. A lack of published data exists in terms of the variability of opening pressure between and within subjects. It is suspected that a simple change in position of a subject during the measurement or change of instrument used contributes to variability in the measurement.

[figure not shown]
### 7.1.9. X-ray Examination of Spine

N/A

[figure not shown]

Page 74

Product: Nusinersen	Statistical Analysis Plan
Study: 232SM203	Version: 3.0 Final

# 10. Pharmacodynamic Endpoints

As detailed earlier NF-L is defined as a secondary endpoint.

In addition, plasma and CSF PK concentrations will be analyzed with plasma and CSF biomarkers to establish PK/PD correlation. PK/PD and exposure-response may also be conducted on efficacy. The results of this study may be combined with other nusinersen studies to perform population PK/PD analyses, including exposure-response analysis.

## **Other Analyses**

Not applicable.

## **Statistical Considerations for Interim Analysis**

Not applicable

Product: Nusinersen	Statistical Analysis Plan
Study: 232SM203	Version: 3.0 Final

# **Changes from Protocol-Specified Analyses**

The secondary endpoint for plasma NF-L comparing Higher dose nusinersen to 12mg nusinersen was changed from Day 29 in the protocol to be Day 64 in this Statistical Analysis Plan

## Summary of Changes from the Previous Version 1.0 of the SAP

Added in the per protocol set definition: Participants who had a previous diagnosis that would confound the data/conflict with SMA.

Added text to Section 6.4.1 to clarify that if baseline is missing, the median used in the imputation will be rounded up to the nearest integer value.

Added clarification to Section 6.4.3 that Ranking based on death will be performed as described earlier for CHOP INTEND. In terms of ranking based on the NF-L, progressively higher ranks will be given to subjects with a greater reduction in NF-L at Day 183.

Removed the analysis of CSF NFL with the joint rank test at Day 64 in Section 6.6.1. Day 64 is not feasible to use since the 50/28mg received a sham procedure at Day 64.

Two sensitivity analyses added to Section 6.1 based on comments from the FDA:

- Use of an ANCOVA model where the variance is estimated in each treatment arm separately for the main analyses of the change in CHOP INTEND and HINE-2 total score to Day 183 comparing sham to Higher dose.
- Implementation of Jump To Reference (J2R) and the joint rank test for the main analyses of CHOP INTEND and HINE2 total score for sham compared to higher dose and 12mg compared to higher dose.

## Summary of Changes from the Previous Version 2.0 of the SAP

Based on comment from FDA added a sensitivity analysis for the main analyses using joint rank test of the change in CHOP INTEND and HINE-2 total score to Day 183 comparing sham to higher dose where the variance is estimated in each treatment arm separately.

